#### Co-Operative Pain Education and Self-management (COPES):

This trial is informed by the widely-recognized gap between evidence of effectiveness of CBT for chronic pain management and equitable and timely access to it. A desire to address these gaps has informed the proposed trial. Our interest in comparing the real-world outcomes of COPES (IVR-CBT-CP) and synchronous CBT-CP is rooted in determining if there is clear evidence of superiority and thus, cause to recommend one treatment over the other. Alternatively, if there is not superiority; then providers can rely on patient preference and local availability to determine what is offered to patients. Additionally, identification of patient characteristics (e.g., age, gender, pain features, co-occurring conditions) that predict or moderate a positive response to CBT for chronic pain (in either form) or induce preferential response to one treatment relative to another can meaningfully guide policy and clinical decisions. Finally, identification of the organizational, provider and patient-level barriers that prevent referral and widespread patient uptake of these approaches could improve our ability to engage patients initially and to sustain their participation over time.

## 2.2 Study Rationale

Evidence related to IVR-delivered CBT for chronic pain. The central proposed intervention, IVR based CBT for chronic pain was recently examined in a non-inferiority trial by our group. The COPES (Cooperative Pain Education and Self-Management) efficacy trial randomized VA patients with chronic back pain to receive either a) in person-CBT-CP: 10 weekly in-person individual CBT sessions with a therapist for chronic pain or b) IVR-CBT-CP: 10 weeks of daily IVR calls with weekly pre-recorded personalized feedback messages about their progress. Patients in both groups received CBT self-care support manuals, and both the “in-person CBT-CP” and “IVR CBT-CP” interventions included 10 CBT modules covered at the rate of one per week that covered the same pain coping skills. Patients in both groups

were also provided a pedometer and instructed to increase their daily step counts by 10% each week. All participants received brief automatic nightly IVR calls to assess pedometer-measured step-counts and other pain-related outcomes. At 12 weeks post enrollment, statistically significant improvements in physical functioning, sleep quality, and physical quality of life relative to baseline occurred in both treatments, with no advantage for either treatment (Figure 1). Post-treatment, 33% of subjects receiving in-person CBT reported clinically meaningful improvement in pain intensity of at least 30%, compared to 19% receiving IVR-CBT ( $p=0.19$ ). For physical functioning/disability, 35% of participants in in-person CBT and 45% in IVR-CBT reported a reduction of at least 30% ( $p=0.43$ ). Additionally, the “IVR CBT” participants reported step count increases that were comparable to the increases observed in “in-person CBT.” Overall, across all participants, an average increase of 2,072 steps per day was observed from baseline to follow-up; this equates to an increase of approximately one mile of walking per day. Additionally, IVR-CBT patients received 2.3 (95% CI: 1.0, 3.6) more weeks of treatment than patients attending in-person sessions, and patients were equally satisfied with IVR and in-person therapy. Finally, participants were proactively assessed each week for study-related adverse events. Forty-six participants experienced 92 related and unrelated AEs (COPES=40, In-person CBT=52). Most related AEs were small increases in pain from exercise. The number of AEs was not significantly different by treatment group ( $p=0.44$ ). Only two serious AEs were reported, but judged by the IRB to be unrelated to study participation.

**Figure 1. Pain Intensity (left panel) and daily steps (right panel) reported among VHA patients with back pain randomized to in-person CBT (red line) vs. IVR CBT (blue line).**

The proposed project will be the first large scale pragmatic trial designed to directly evaluate the relative effectiveness of an asynchronous CBT intervention for the management of chronic musculoskeletal pain delivered in “real life” clinical practice settings compared to “standard” CBT involving intensive outpatient psychotherapy with providers previously trained to deliver this treatment. As such, this project stands to change the care of Veterans, and by extension, others with chronic musculoskeletal pain, by demonstrating the feasibility of a low burden, cost-effective intervention that overcomes many known organizational, provider and patient-level barriers to accessing effective pain self-management interventions.

The clinical impact of the treatment will be evaluated in terms of its effectiveness, reach and cost, both in absolute terms and relative to other available treatments, thus providing invaluable information beyond that obtained from our prior efficacy and implementation trials. Our approach was chosen to identify the most effective treatment that patients will engage in and that is feasible for the healthcare system to provide.

### **3. STUDY DESIGN**

This is a randomized hybrid type 1 pragmatic superiority trial comparing a technology-based form of CBT-CP that patients can do from their homes (COPES IVR-CBT\_CP) versus synchronous CBT-CP delivered by a VA clinician. to examine the strengths and weaknesses of an IVR-based form of CBT-CP called Co-Operative Pain Education and Self-management (COPES) versus synchronous CBT-CP provided by clinicians previously trained through VHA’s evidence-based psychotherapy program.

[figure not shown]
Eligible patients will be identified from the EHR. The electronic health record will be used to collect information on referred patients for analysis and contains reliable information on diagnoses, medications prescribed, and patients’ clinical history and demographics, a limited number of demographic items will be confirmed via telephone screening.

The study will occur in 9 Women’s Health-Practice Based Research Network (WH-PRBN) sites selected during the UG3 planning period on the basis of site quantitative metrics and a diagnostic process evaluation. The study sample will be drawn from patients with an electronic health record (EHR) derived a) musculoskeletal diagnosis and b) 2 or more reports of pain of  $\geq 4$  on the pain numeric rating scale (NRS) occurring within the past 12 months. After receiving a referral from a site clinician or patient self-referral, study staff at the centralized coordinating center at VA Connecticut Healthcare System (VACHS) will contact patients by telephone, and assess patient interest and consent eligible patients. All randomized patients will be asked to complete an automated telephone assessment prior to beginning treatment and 1, 4, 6, and 12 months after beginning, through the study IVR system.

Patients randomized to COPEs (IVR-CBT) will be enrolled in the daily IVR monitoring system and participate in 10 weeks of pain self-management treatment with asynchronous therapist feedback skills as well as completing the assessments over 12 months. COPEs treatment is managed by the coordinating center at VACHS. Patients who are randomized to in- person CBT-CP will receive treatment at their local VA by a local CBT-CP clinician and will also participate in completing assessments on the IVR system for a duration of 12 months at the time points specified above.

A total sample size of 610 subjects (305 per group) would provide 80% power to detect a mean difference in BPI interference of 0.55 between COPEs and CBT-CP at 4 months using a two-sided t-test at significance level  $\alpha=0.05$ . To account for an expected attrition rate of 20% in each group, we will enroll a total of 764 participants (382 per group) with a target of half of the participants being female.

Below is diagram of participant flow through the project:

#### 4. SELECTION AND ENROLLMENT OF PARTICIPANTS

**Participants.** The study sample will be drawn from patients with an EHR derived a) ICD-10 pain-related musculoskeletal diagnosis and b) 2 or more reports of pain of  $\geq 4$  on the pain numeric rating scale (NRS) occurring within the past 12 months, as used in prior trials and who are

receiving care at a selected site within the WH-PBRN. Data from our Musculoskeletal Diagnoses (MSD) cohort show 5,237,763 patients in VHA care had a musculoskeletal diagnosis between 2000-2011 with the most common diagnoses being non-traumatic joint disorder (27%), back disorder (25%), and osteoarthritis (21%). We expect the incident cases captured after 2011 to follow this same pattern. Approximately 20% of Veterans in the cohort had 2 or more concurrent MSDs. Among patients entering the cohort in 2011, 47% reported a score of  $\geq 4$  on the 0 (no pain) to 10 (worst pain imaginable) on the pain intensity NRS at an outpatient or inpatient encounter. In 2011, 7.7% of patients in the MSD cohort were women, 74% non-Hispanic White, 15% were African American, and 5% were Hispanic. Given the prevalence of chronic musculoskeletal pain in VHA, there will be more than an adequate number of eligible patients to meet our enrollment target of 764. Because we have a sub-aim to test for differences in outcomes between men and women and women only represent approximately 8% of VHA patients, we will oversample women. Our final sample target will be 50:50 men to women. We will not stop recruitment of male Veterans if we exceed the 382 target number, but will continue to recruit both men and women until the total enrollment goal of 764 is reached. We have elected to spread recruitment over 9 sites throughout the WH-PBRN so that enrollment targets for women will be manageable at each site ( $n=382$  total women over 9 sites= $42$  women per site over 3 referral years). As a comparison, in our COPEs efficacy trial we recruited 28 women over 4 years, though we were not specifically attempting to increase recruitment of women. In this context, with specific focus on recruiting women, we believe that 42 per site is feasible. The number of eligible Veterans who actually engage in COPEs IVR-CBT-CP or in person CBT-CP and how many sessions they attend will be examined in the proposed work (see Data Analysis 9.6 “Engagement”).

Based on our UG3 work, we believe that the optimal number of sites is fewer than the originally proposed 20 sites. Proposing 20 sites was not based on a power analysis, but a strategy to spread the recruitment and treatment burden over more sites. This is not a cluster randomized trial and reducing the number of sites will not compromise our power to detect differences in the primary outcome. Moreover, as shown in Table 2, even a much smaller number of sites than originally planned will still result in reasonable recruitment targets for each site. Nine sites would require each site to enroll only 2.3 participants per month. Local site clinicians would need to provide treatment for half that number because the remainder would obtain treatment from clinicians at VA Connecticut through the IVR-based CBT-CP. We believe that approximately 9 final sites will be the most advantageous number for striking a balance between meeting enrollment targets and the additional effort required to manage and oversee more sites. Additionally, we believe that securing the most interested and well-positioned sites as opposed to sites with less interest and marginal availability of clinicians may be the most feasible and practical approach. We have 4 additional back up sites that can step in quickly if one of the initial sites is no longer eligible.

Number of sites	Total # of participants per site (total N=764)	# participants per month per site over the enrollment period
5	153	4.3
9	85	2.3
10	76	2.1
12	64	1.8
14	55	1.5
16	48	1.3
18	42	1.2
20	38	1.1

Table 2 showing recruitment by site for various numbers of sites

Despite having fewer sites than originally proposed, we believe that the selected sites are sufficiently diverse to ensure our findings will be generalizable. The sites represent all major geographic regions of the US except the southwest and sizes in terms of patient populations. According to the data provided by the WH-PBRN, the sites have a range of rurality from highly urban (Jess Brown in Chicago) to primarily rural (Jackson, MS). To further increase rural patient representation, we will recruit patients from community-based outpatient centers (CBOCs) affiliated with the selected sites. Selected sites range from predominantly white like Ann Arbor (71.3%) and Puget Sound (69.1%), to sites with majority black populations like Jackson, MS (64.1%), Jesse Brown (60.7%), and those with a plurality of black patients (Charleston, SC 48.7% black and 36.7% white). Hispanic populations range from 2.6% to 10.9% across sites, with Asian populations ranging from 0.2%-3%. The Oklahoma City site has a relatively high percentage of American Indian patients (2.8%).

Eligible patients will be identified from the EHR or patient self-referral (see 4.3 for details). The electronic health record will be used to collect information on referred patients for analysis and contains reliable information on diagnoses, NRS pain intensity score collected at medical center visits, medications prescribed, and patients' clinical history and demographics. The investigators on this team have experience conducting custom queries for research purposes, reviewing and managing data related to pain and its outcomes, and using informatics to identify patients who meet our study criteria. (Section 9.6 Data Analysis-Engagement)

#### 4.1 Inclusion Criteria

Consistent with the guidelines for pragmatic trials the eligibility criteria will be as inclusive as possible so that the study cohort represents the population of patients with chronic musculoskeletal pain receiving care in VHA. Unlike most trials of non-pharmacological interventions for chronic pain, patients with history of substance abuse disorders or active use disorders will not be excluded. Eligibility criteria are designed to identify patients with: (1) a pain-related musculoskeletal diagnosis indicated by an EHR identified ICD10 code ( i.e. M54.5, M54.2, M25.561, M25.562, M25.511, M25.569, M25.512, M19.90, M17.0, M17.9, M54.16, M25.551, M51.36, M25.519, M25.552, M06.9, M79.673, M72.2, M19.91, M17.11, M79.671, M79.672,

M17.12, M48.02, MS4.9, M79.7, M54.12, G89.4, F45.42) ; (2) presence of chronic pain of at least moderate severity (two or more EHR NRS pain scores of  $\geq 4$  in for a period of 12 months with 30 days between occurrences); (3) ability to participate safely in the walking portion of the intervention as evidenced by patient-reported ability to walk at least one block and absence of diabetic foot ulcers at the time of the enrollment call; (4) availability of a touch-tone land-line or cellular telephone.

## **4.2 Exclusion Criteria**

Exclusion criteria will include (1) current inpatient psychiatric hospitalization for detoxification of alcohol or drugs or acute psychotic episode; (2) receipt of hospice or end-of-life palliative care because we do not believe these participants could meaningfully participate or benefit from CBT-CP and short survival time will likely limit their time in the trial leading to lowered treatment dose and high probability of missing outcome data or dementia-related diagnosis (F02.81, A81.00, F02.80, F03.90, A81.01, A81.89, A81.9, F03.91, F10.27, A81.09, A81.2, F01.50, F19.97, F01.51, G30.0, G30.1, G30.8, G23.1, G90.3, G30.9, G31.01, G31.83, G31.09) as dementias are marked by impaired memory, executive function, and inability to learn new information we do not believe these patient swill be able to learn new pain management skills and therefore they will not benefit from CBT-CP; (4) vision or hearing deficits that would impair participation verified by patient report at the time of the enrollment call (5) current participation in CBT-CP; and (6) any medical intervention that would cause a meaningful increase in pain such as surgery, chemotherapy, radiation therapy.

## **4.3 Study Enrollment Procedures**

Recruitment. Potential participants will be recruited either by self-referral (i.e., opt out letters, toll free number from advertisements) or by provider referral. To promote self-referral, informational posters, flyers, and business cards will be placed at participating sites. Veterans who are interested in participating may refer themselves by contacting VA Connecticut study staff using a toll-free number listed on the materials. For provider referral, patients will be recruited during primary care or mental health visits in the study settings. We will use the national corporate data warehouse (CDW) data obtained from the VA electronic health record (EHR) to identify eligible patients based on ICD10 musculoskeletal diagnosis code, present of at least 2 pain reports of 4 or great in the prior 12 months, absence of palliative or hospice care, and absence of dementia diagnosis. The national CDW database will be accessed by a computerized referral alert built during the UG3 period and installed at each of the recruiting sites. The alert will query the CDW data automatically. An EHR alert to the treating provider will be visible to the

treating provider during a scheduled clinic appointment. The EHR alert will contain three elements: Notification that the patient could benefit from CBT-CP, brief messages describing CBT for pain broadly (not specifying anything about either treatment under consideration, simply stating that they are eligible for CBT for chronic pain), suggestions for presenting the referral to the patient, and a hyperlink that will automatically place the inter-facility referral to VACHS study staff when clicked. We have chosen not to discuss the possibility of referral to different forms of CBT-CP because we want the trial to mimic routine care and in routine care there would not be randomization and patients may not be able to choose their specific form of treatment (e.g., in-person, telehealth, individual, group). In cases where visit time is short or if for any reason clinicians do not want to introduce the referral to COPES/CBT-CP at that visit, providers may click a link that requests they be notified again at the patient's next visit. When patients agree to be referred or to speak to study staff to learn more about CBT for chronic pain, the provider will simply click the hyperlink embedded in the alert to generate an inter-facility consult to the study staff.

Enrollment and randomization. Patients will be contacted, screened, enrolled, and randomized in the same way whether they are self-referred or provider referred. After receiving a referral from a clinician at a study site or a voicemail from a patient self-referral, VA Connecticut study staff will contact patients by telephone, and using a semi-structured interview, assess patient interest, patient's self-reported ability to walk at least one block, presence of a landline or cellular telephone, and absence of vision or hearing loss that would interfere with participation (to confirm eligibility criteria not reliably contained in the EHR), use of complimentary and integrative health (CIH) modalities and answer any questions patients have about the intervention (see attached script) as well as review their VA medical record to confirm eligibility. If a patient is willing to obtain treatment, study staff will read the approved consent language contained in the information sheet. Patients will be specifically asked about consenting to the audio recording of their voice if they leave a message for their study therapist. The information sheet will be available to patients on our study website. The website is a resource for patients and has copies of the information sheet, the patient handbook and audio files of the relaxation exercises. Patients do not need to login and it does not collect, hold or request any PHI or patient data. Use of the website will allow patients to view a copy of the information sheet without the delay of prior mailing. If patients do not have access to the internet or if they would prefer to have a physical copy prior to consenting, we will mail them a copy and contact them at a later time for consenting. Staff may email the patient

the link to the study website or reminder for scheduled assessments upon request. Email addresses used for communication will be identified by the patient during routine staff telephone screenings or reminders. No PHI will be included in email communication. Veterans for whom an email address is available can opt-out at any time of email communication by contacting our 1-800 number. The email to Veterans will state specifically that they are to not respond as the email address is not monitored and anything they reply is not protected and the VA is not liable for. Patients will be told that they will be asked to complete an automated telephone assessment prior to beginning treatment and 1, 4, 6, and 12 months after completion in order to evaluate the treatment program. Following consent patients will then be enrolled in the study IVR system so that baseline and follow-up assessment can be obtained. After completing the baseline assessment, participants will be randomized. Patients will select a convenient time of day to receive their assessment phone calls and the IVR system will automatically leave a reminder message 1 day prior to their scheduled assessments. Patients randomized to COPES (IVR CBT-CP) will receive automated calls each evening between 6pm and 10pm at a time pre-selected by the patient to ensure that each call captures the full 24-hour reporting period. On evenings when participants miss their scheduled call, the IVR system will call again 2 additional times. Alternatively, participants may initiate a call into the system themselves. COPES patients will be instructed to go to the study website to obtain access to the patient handbook that accompanies the treatment, or one will be mailed to patients who do have Internet access. A pedometer will be mailed to COPES patients so they can engage in the graduated walking program. Patients who are randomized to synchronous CBT-CP will be referred to a site CBT-CP clinician by study staff using an electronic interfacility consult (IFC). VA Connecticut study staff will initiate an IFC for each participant randomized to synchronous CBT-CP. This IFC will be sent to the corresponding local site contact and appear in the usual referral workflow (i.e., it will appear in the same pathway as a non-study related referral to CBT for chronic pain). The VA electronic health record system automatically tracks IFCs and the referral source is automatically notified when a referred patient's consult is either declined or scheduled and closed. This will allow us to track the disposition of referred synchronous CBT-CP participants.

Randomization Participants will be randomized in a 1:1 ratio to one of the two treatments (COPES or CBT-CP). The randomization sequence will be generated by the study statistician using statistical software and concealed in the study database until the time of randomization. Randomization will be stratified by site and gender

and will be done according to a permuted block design with variable block size (4 and 6) to maintain balanced treatment assignment.

A waiver of informed consent for recruitment purposes has been obtained, for recruitment and initial study screening.

A waiver of documentation of informed consent has been obtained for the intervention. The information sheet will be available on the study website, as explained, or participants will be mailed an information sheet if they request it. Certificate of confidentiality language will be included.

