#### CBT-CP Interventions.

#### COPES (IVR-CBT-CP)

Overview. COPES (IVR-CBT-CP) is a 10-week, IVR-facilitated program of CBT for chronic pain. The primary components of the intervention include: 1) a self-help handbook containing the rationale and instructions for using eight pain self-management skills, and their corresponding weekly skill practice goals; 2) a pedometer-facilitated walking program; 3) daily, automated IVR calls to collect patient-reported pain intensity and pain interference, sleep quality, pedometer-measured step count, and adherence to the pain coping skill practice ratings; and 4) weekly, two to four minute pre-recorded, personalized therapist messages based on participant IVR-reported data. The COPES IVR system provides participants the ability to automatically connect to the Veteran Crisis Line during any call. In this study, COPES will be centrally delivered from the VA Connecticut site. Participants will be given up to 14 weeks to complete treatment to allow for missed sessions

(vacations, illness).

Intake and materials. Each weekly IVR module will feature a single self-management skill (e.g., paced physical activity, stretching, or relaxation) reinforced via a companion chapter in the patient handbook. The handbook, developed for the initial COPES efficacy trial and refined prior to the ongoing COPES implementation trial, is written at the 6th grade reading level and features design strategies to enhance engagement and readability. The manual will assign a specific goal each week that promotes practice of the module's coping skill (e.g., practice deep breathing for 5 minutes each day this week). The participant will be instructed to practice that week's skill each day of the week and report via daily IVR assessment their daily skill practice completion (0=not at all completed to 10=totally completed). Participants will have access to a patient handbook through the COPES website. If patients do not have Internet access the handbook will be mailed to them. Participants will also be mailed an Omron Go Smart Model HJ-320 pocket pedometer to facilitate their participation in the walking portion of the treatment.

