Process evaluation. In order to refine and evaluate our implementation of the proposed interventions, we will conduct a formative evaluation, with implementation-focused, progress-focused, and interpretation phases. We will use semi-structured telephone, or in-person interviews conducted by a trained research assistant under the supervision of a qualitative expert. Interview guides will be developed using constructs and questions derived from the Consolidated Framework for Implementation Research (CFIR), refined based on our experience in the COPES implementation trial and tailored to the informant group being interviewed (mental health provider, primary care provider or administrator). The interview guides are being developed and piloted in the context of another approved study and when complete, the guides will be submitted to the cIRB for approval prior to use. Interviews will be audio-recorded and professionally transcribed by a VHA-approved contractor. Participants in each of the stakeholder categories (i.e., providers and administrators) will be recruited by in-person recruitment strategies or email solicitations with the assistance of the WH-PBRN site lead. Staff interviews will be conducted with clinical staff who provide clinical care and who we anticipate will be directly involved in patient referral including primary care providers (n=2 per site), mental health providers (n=2 per site), and administrators (n=2 per site). Providers will be emailed an information sheet or asked to view it on the study website which details their participation. Interviewers or staff will go over this with the provider participant and will specifically ask about consenting to the audio recording of their voice. We will record the provider's confirmation of this consent.

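### Control patients can reach the COPES handbook and relaxation audio on the open study website, and the plan neither restricts nor records this.

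*Combined protocol and SAP*

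**What the plan says.** Section 4.3 says that the study website "has copies of the information sheet, the patient handbook and audio files of the relaxation exercises. Patients do not need to login", and section 11.2 repeats this. It adds that the site holds no patient data: "Patients do not need to login and it does not collect, hold or request any PHI or patient data".

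The site serves two purposes. Before consent it is a source of the written information sheet: "Use of the website will allow patients to view a copy of the information sheet without the delay of prior mailing". Staff may also email "the link to the study website or reminder for scheduled assessments upon request". After randomisation it is where the experimental arm gets its manual: "COPES patients will be instructed to go to the study website to obtain access to the patient handbook that accompanies the treatment". The Précis and section 5.1 speak of a COPES website rather than the study website, but section 4.3 makes clear that the handbook is on the latter.

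The Précis and section 5.1 list four primary components of COPES. The first is "a self-help handbook containing the rationale and instructions for using eight pain self-management skills". The others are the pedometer walking program, the daily IVR calls and the weekly recorded therapist feedback. The relaxation audio is not listed separately.

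No section limits handbook access by arm. The schedule in 6.1 has no item on handbook use. Nor do the indicators of separation between arms in 9.4, which are dose, engagement, minimal dose, time to treatment initiation and quality.

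**The concern.** Sections 9.1 and 9.4 expect COPES to do better because control patients will receive less treatment and start it later. A self-help manual that those patients can open is an avoidable leak in that contrast. Usual practice does not explain it: the plan does not describe the COPES handbook as part of routine CBT-CP, and it is the trial's own website that makes it reachable.

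The leak would also be invisible. Control-arm dose and engagement are counted from sessions in the health record (section 5.4), so a control patient working through the handbook at home would still count as having had no treatment. The 9.4 indicators could show the arms diverging while their outcomes drew closer.

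What is at stake is power and the meaning of a null result. Section 2.1 says that if superiority is not shown, the choice can rest on patient preference and local availability. That conclusion is less secure if some of the similarity could come from shared material that nobody measured.

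**Working it through.** **Inputs from section 9.2:** SD 2.4, 305 evaluable per arm, two-sided alpha 0.05, target difference 0.55, stated power 80%.

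**Inputs not in the documents (assumptions):** u, the share of control patients who use the handbook, and h, the share of the between-arm effect that use removes in such a patient.

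**Step 1: reproduce the plan.** Standard error of the difference = 2.4 × √(2/305) = 0.1943. Ratio = 0.55/0.1943 = 2.830. Normal approximation: Φ(2.830 − 1.960) = 80.8%. The two-sample t-test gives 80.7%. The plan's 80% reproduces.

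**Step 2: apply dilution.** If use is confined to the control arm, the control mean moves toward the COPES mean by u × h × 0.55, so the diluted difference is 0.55 × (1 − u × h). Power is then about Φ(diluted difference/0.1943 − 1.960). The t-test values use the same standardised difference.

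| Assumed u, h | u × h | Difference | Power, normal | Power, t-test |
|---|---|---|---|---|
| none | 0 | 0.550 | 80.8% | 80.7% |
| 10%, 10% | 1% | 0.545 | 80.0% | 79.9% |
| 10%, 25% | 2.5% | 0.536 | 78.8% | 78.7% |
| 10%, 50% | 5% | 0.523 | 76.7% | 76.6% |
| 20%, 50% | 10% | 0.495 | 72.1% | 72.0% |
| 50%, 50% | 25% | 0.413 | 56.5% | 56.3% |

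For the 10% row: 0.55 × 0.90 = 0.495; 0.495/0.1943 = 2.547; Φ(2.547 − 1.960) = 72.1%.

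**Step 3: read the table.** The sample size leaves almost no headroom: a 1% dilution uses it up. Losses stay within about four percentage points up to 5% dilution. The bottom row needs half of all control patients to use the handbook and each to lose half of the between-arm effect; it marks the end of the assumed range and is not a forecast. Therapist clustering is left out, because the plan states its power at 0.55 on the simple t-test.

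**The case against.** A reader might infer that every candidate and the local providers are sent to this site. The documents do not say so. Section 4.3 has staff read the consent language by telephone, the link is emailed only on request, and a paper copy is mailed to those who want one or lack internet access. The provider route is narrower still. In section 9.6, under Process evaluation, "Providers will be emailed an information sheet or asked to view it on the study website", but this covers only interviewees (two primary care providers, two mental health providers and two administrators per site), has email as an alternative, and does not say that they treat control participants.

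A reader might also infer that control patients are given a core part of COPES. They are not: only COPES patients are told to fetch the handbook. Being able to reach it is not the same as being provided with it.

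The strongest counter-argument concerns size. Control patients are offered active CBT-CP with similar skills (section 5.2), and the therapist manual for it is already public. In the earlier efficacy trial both arms received self-care manuals (section 2.2), so the handbook was not the contrast there. The expected advantage in 9.1 and 9.4 comes largely from dose, timing and burden, and the other three COPES components are not described as available on the website. It is also conjecture that under-treated control patients would be the ones to use a handbook alone; they may be the least inclined to.

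All of this stands and limits the likely effect. It does not remove the gap. Overlap with the offered therapy matters least for control patients who attend few or no sessions, and the plan has no means of showing that exposure was small.

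**Conclusion.** The point holds as a gap in safeguards: one of the four primary COPES components is reachable by control patients without login, and their use of it is neither restricted nor recorded. Any benefit from such use would most likely act toward no difference. It bears on power and on interpreting a null result, and would not make COPES look better than it is.

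The documents do not support a claim that the contrast is in fact diluted, or by how much. They give neither the rate of control-arm use nor the handbook's share of the effect, so the fall from 80.7% to about 79% (2.5% dilution) or about 72% (10% dilution) shows sensitivity and is not an estimate. The design figures (305 per arm evaluable, 764 enrolled) need no change on this account. The case for acting is that the remedy costs very little.

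**What to change.** Keep only the information sheet on the public page. Put the handbook and relaxation audio on a separate unlisted page, or behind one shared code, given only to COPES participants after randomisation; continue mailed copies as now. Amend sections 4.3 and 11.2 to match. No personal login or patient data is needed.

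If exposure is to be described, add one item on handbook use to the existing month 4 IVR assessment for both arms, after the BPI items so that it cannot affect the primary outcome. This also covers participants randomised before the change, provided they have not yet reached month 4. Website access counts would not serve, because the site collects no patient data and the counts cannot be split by arm.

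Cost: a web-page change, a short protocol amendment and, if adopted, one extra question. COPES participants need a second link or code, and a code can be passed on, so access is reduced rather than eliminated. The documents do not state how far enrolment has progressed; the later it is, the less the page change achieves and the more the month 4 item matters.
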